Study assessments		X	X	X	X	X	X	X	X	X	X	X	X	X	X	X
Data Management Activities																
Final Database Ready																M-11
Final Session Recording Collected															M-7	
IE Coding of Tapes for Fidelity & Differentiation	Ongoing for consultation purposes														X	X
Data Analysis																X
Preparation of manuscripts																X

9) **Study Endpoints***

The primary study outcome will be treatment response. Response will be defined as a Clinical Global Impression-Improvement (CGI-I) of 1 or 2 at 16 weeks after treatment initiation and at the 3 month follow-up. Secondary outcomes will include scores on the Children's Global Assessment Scale (CGAS), Screen for Child Anxiety Related Emotional Disorders-Youth and

Parent Reports (SCARED/-P), and the Mood and Feelings Questionnaire-Self & Parent Reports (MFQ), as well as diagnostic status on Anxiety Disorders Interview Schedule for the DSM-5, Child Version, Child and Parent Report Forms (ADIS-5-C/P).

The following measures will be taken to monitor data relating to safety:

Throughout the study, trained study staff will monitor participants' risk of harm. It is possible that participants' clinical data might indicate, for example, that a parent or adolescent is at risk (e.g., adolescent or parent reports suicidal ideation, or an adolescent's physical safety or well-being is in question). In order to address such situations, all study therapists and staff will be thoroughly trained in the ethics of conducting research with human participants, and will be thoroughly educated about the project's data safety and monitoring procedures. All such incidents will be reported immediately to the principal investigators, and, if necessary, to the local IRB according to their policies.

In addition, we will use the short version of the Columbia-Suicide Severity Rating Scale (C-SSRS) at baseline, 16 weeks, and 3 month follow-up and following any evidence of suicidal ideation or significant adolescent deterioration. The C-SSRS allows the IE to gather information on suicidal behavior, suicide attempts, and presence and intensity of suicidal ideation. The information will be used to identify adolescents possessive of active suicidal ideation, intent or plan that may need to be excluded due to needs for more acute care.

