community. This assessment will include completion of some or all of the questionnaires/procedures listed in the “Pre Treatment” column in Table 2 and described in additional detail below. Randomization will take place following this first assessment once subjects have been deemed eligible for participation. If a participant is unable to begin treatment within 4 weeks of their initial baseline assessment, an abbreviated baseline re-assessment may be conducted prior to the start of treatment. This re-assessment will include review of the symptoms previously endorsed on the ADIS-5-C/P, SCARED, MFQ, YOQ, SDQ, DTS, and Avoidance Hierarchy (see Measures, below).

If any study assessment is to occur at the University of Miami, parents/guardians will be emailed a “paybyphone” link to register their car for parking through the University’s Parking and Transportation department. They may be asked to supply their license plate number so that study staff may register their car for them in the case of user or system error. License plate numbers will be discarded following termination of study participation, and will not be used for research purposes.

At every therapy session, some or all of the assessments/questionnaires listed in the “Every Session” column in Table 2 will be completed. Additional assessments will take place approximately 8 (mid-treatment) and 16 weeks (post-treatment) after treatment initiation, as well as 3 months after the post-treatment assessment. All efforts will be made to have these assessments take place within a specified time window in relation to the 8, 16, or 28 week time-point date. The windows allow for data collection up to two weeks before the time-point date and up to 2 weeks, 4 weeks, or 8 weeks after the time-point date for the mid-treatment, post-treatment, and follow-up evaluations respectively, although data may still be collected should participants miss this window. During these visits, some or all of the measures detailed in the respective assessment point columns in Table 2 will be administered. With the exception of the computer-based tasks (e.g., the BIRD task), all adolescent- and parent-report measures will be available in English and in Spanish. The Spanish translations of these measures will be submitted in an amendment prior to initiating data collection.

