CGI-S	IE		X		X	X
CGI-I	IE				X	X
CGAS	IE		X		X	X
SCARED	C, P		X	X	X	X
MFQ	C, P		X	X	X	X
YOQ	C, P	X (UP-A, TAU+ Only)	X	X	X	X
SDQ	C,P		X	X	X	X
Avoidance Hierarchy	C, P, IE		X	X (C, P only)	X	X
PHQ9	P		X	X	X	X
GAD7	P		X	X	X	X
CCNES	P		X	X	X	X
DTS	C, P		X	X	X	X
S-EMBU	C, P		X	X	X	X
BIRD	C		X	X	X	X
CEMS	P		X	X	X	X
CEASE-A	C		X	X	X	X
EASI-A	C		X	X	X	X
PANAS-C	C		X	X	X	X
WAI	C, T			X	X	
BTPS	P		X			
CSQ	C, P			X	X	X
HURTE-II	C,P		X ³	X ³	X ³	X ³

Session Report Form	T	X				
EBPAS	T		X ¹		X ²	
ASA-MF	T		X ¹		X ²	
MFA	T		X ¹		X ²	
TCU-ORC	T		X ¹			
UP-A Knowledge Check	T*				X ²	
Therapist Background	T		X ¹			

C = Child, P = Parent/Caregiver, IE = Independent Evaluator, T = Therapist

1. Administered to the clinician before they start treating their first study case.
2. Administered to the clinician after they complete their first study case.
3. May be administered to participants to screen for Hurricane Irma related stressful life events at the first contact the study has with the participants after the storm.

*Administered to clinicians randomized to the UP-A condition only

Description of Measures and Data Collected:

Screening/Baseline Measures:

- **Columbia-Suicide Severity Rating Scale (C-SSRS).** The C-SSRS is a semi-structured interview designed to screen for presence and severity of suicidal ideation and suicidal behavior. There are parent and child report versions, as well as versions designed to assess suicidality at baseline (which assesses the last 6 months for study inclusion) and for later assessment points (which assesses ideation and behaviors since the last assessment).
- **CRAFFT Screening Test:** The CRAFFT is a 9 item screening questionnaire, with yes and no questions related to substance use. The questionnaire is used as an interview administered by the independent evaluator.
- **Family Background and Medical History Form:** The project created a form to gather background information, such as demographic and educational information, as well as medical history data.
- **Youth Demographics Form:** The project created a form to gather race/ethnicity, gender, and sexual orientation information directly from adolescents, as parents may report these items differently than adolescents.
- **Family Contact & Locator Form:** This form will be used to gather contact information and other identifying information, as well as additional people who could locate the family if the project loses track of them.

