All project staff will be educated about the importance of confidentiality, and trained on procedures used to protect this within the study. Information about participants will be kept strictly confidential (to the extent permitted by law) and information about participants will not be released without a signed release form by the child's caretaker.

Data Analysis Plan:

We plan to use GLMM (multilevel modeling, MLM, with a logistic linking function) to examine treatment effects on the dichotomous primary outcome ("response", defined as CGI-I of 1 or 2). Additional clinician-rated (e.g., CGI-S, CSR) and questionnaire-based (e.g., SCARED, MFQ) outcomes are all continuous measures and will be analyzed using traditional MLM.

13) Provisions to Monitor the Data to Ensure the Safety of Subjects*

The Principal Investigators, in accordance with the policies outlined by the University of Miami and UConn Institutional Review Boards (IRBs), are responsible for ensuring the safety of participants and the integrity of research procedures. Throughout the study, the PIs will work with all staff, Co-I's, and grant consultants, to ensure compliance with the study's procedures and data and safety monitoring plan. Finally, a Data Safety Monitoring and Board has been appointed to monitor progress of the study and at least annually (more frequently if needed). The Board members are [name] and [name] from the University of Miami and [name] from UConn.

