Procedures to monitor participant Safety: Throughout the study, the PIs and all study staff will monitor participants' risk of harm, as described above under 9) Study End points. Any evidence of risk of self-harm will be reported immediately to the principal investigators. When possible, at times when patients are seen for the study, a trained mental health professional will be present and available at the clinics to take appropriate measures; at all other times the principal investigators or post-doctoral fellow will help the assessors generate a safety plan. In the case that abuse or neglect is discovered, appropriate measures will be taken, in accordance with the laws of Florida or Connecticut. Prior to making this report, every effort will be made to inform the family first and discuss the situation with them. However, if the family cannot be reached, the report will still be made promptly, as required by Florida or Connecticut statutes. All families will be informed of the limits of confidentiality during the consent process.

If clinical or questionnaire data indicate that a child is showing a notable decline in functioning during the course of the study, this will be discussed with the child's clinician and caregiver and the child will be referred for additional and/or alternative treatment if appropriate.

Procedures to report any Adverse Event or Unanticipated Problem during the study: Throughout the study, the PIs will be responsible for reviewing and reporting adverse events occurring during the study to their local IRB. If any type of adverse event

occurs, the PIs will report that event to the Miami and/or UConn IRB according to the local IRB policies. If an unanticipated problem occurs to compromise the data or confidentiality of the data storage plan (e.g., a break-in to the laboratory space), the PI will notify the IRBs as well as any participant potentially affected by the event.

14) Withdrawal of Subjects*

Participants and their parents/guardians may be withdrawn from the study without their consent if they are withdrawn from clinical care in the CMHC. Should the client be terminated or transferred in accordance with the local clinic policy, he/she will be withdrawn from the study. In addition, participants may be withdrawn for the following reasons:

- Parent/guardian no longer available to participate with the adolescent.
- Failure to adhere to clinic guidelines and/or clinician guidelines.

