- The participant is no longer able to attend clinic visits or complete research assessments.
- There may be other reasons that are unforeseen at this time.
- The clinician and/or evaluator determine, during interim treatment assessments, that an emotional disorder treatment focus is no longer appropriate/sufficient. If this determination is made by the evaluator, the clinician must also agree that emotional disorder focused treatment is no longer appropriate/sufficient and alternative or additional care is necessary.
- During the course of treatment, the adolescent begins an outside psychosocial intervention similar to that given in the study, or one that the investigators feel may be confounding.

Those participants who voluntarily withdraw from treatment may be asked to complete 8 week, 16 week, and 3 month follow-up assessments for data collection purposes, if appropriate.

Clinicians may be excluded from the study for any of the following reasons:

- They leave the clinic and are no longer seeing clients at the CMHC.
- They are unable to attend and/or participate in training and consultation meetings.
- They are determined inappropriate for the research study (i.e. failure to adhere to treatment, failure to adhere to study procedures).

In the event that a clinician is withdrawn or voluntarily withdraws from the study, clients who are still in treatment will be offered to transfer to another study clinician if appropriate. All clinicians will be asked to consider the best interests of the adolescents when withdrawing from the study, and encouraged to complete treatment with study clients before withdrawing.

15) Risks to Subjects*

There are no physical risks associated with participation in the study. There are minor psychological risks to child and caregiver participants. During assessment procedures, there may be some risk of discomfort, irritability, or anxiety resulting from discussion of personal or emotion-provoking subjects. However, this risk is not greater than that which occurs in the usual clinical evaluation process. Participants and their parents/guardians may experience mild inconvenience from having to complete additional research assessments which may take additional time.

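### The primary logistic GLMM has no missing-data step: a youth with neither CGI-I rating adds nothing, week-8 scores go unused, and progress-related loss that differs by arm would bias the responder comparison

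*Combined protocol and SAP*

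**What the plan says.** Section 9 (Study Endpoints) makes the primary outcome a "Clinical Global Impression-Improvement (CGI-I) of 1 or 2 at 16 weeks after treatment initiation and at the 3 month follow-up". Table 2 in section 10 schedules CGI-I at those two visits and no others. CGI-S and CGAS are also taken before treatment, but not at week 8.

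The symptom questionnaires follow a fuller schedule. The SCARED row reads "SCARED C, P X X X X": youth and parent report before treatment, at 8 weeks, at 16 weeks and at follow-up. MFQ, SDQ and the research administration of the YOQ have the same four visits in every arm.

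The whole primary analysis is one sentence of section 12, which proposes a GLMM with a logistic link "to examine treatment effects on the dichotomous primary outcome". The sentence after it assigns the continuous outcomes to ordinary multilevel models. The plan gives no analysis set, visits modelled, covariates, random effects, missing-data method or sensitivity analysis. Missing data come up only as a reason to administer measures by computer (section 12) and as a quality-assurance topic for Steering Committee calls (section 18).

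On loss of youths, section 14 says: "Those participants who voluntarily withdraw from treatment may be asked to complete 8 week, 16 week, and 3 month follow-up assessments", and only where appropriate. It also says: "Should the client be terminated or transferred in accordance with the local clinic policy, he/she will be withdrawn from the study".

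**The concern.** A model for CGI-I response learns only from youths who have at least one CGI-I rating. The outcome has no baseline or week-8 value, so a youth lost before week 16 and not seen at follow-up leaves no outcome row. That youth's SCARED, MFQ, YOQ and SDQ scores up to week 8 may show how treatment was going, but nothing in the stated model brings them in.

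This matters if the link between poor progress and loss differs by arm. The design offers routes to that. The YOQ warns clinicians of failing progress only in TAU+ and UP-A, and Hypothesis 3c expects engagement to differ between TAU and the two YOQ arms. Clinic discharge, and withdrawal because an emotional-disorder focus no longer suffices, can both follow poor progress. If non-responders disappear more in one arm, that arm's observed responder rate is too high. The primary comparison then moves in a direction the observed CGI-I ratings cannot reveal.

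**Working it through.** **Inputs from the documents.** Target 222 adolescents (section 6), allocated 1:1:1 (section 10): 222/3 = 74 per arm. No response rate, power, alpha or dropout rate is given, so 222 cannot be re-derived. Section 24 speaks of 150 enrolled per site (300 in all) and 222 completing treatment, which would be a loss of 1 − 222/300 = 26%. Section 6 instead describes the 300 as recruited and screened. Every response and dropout rate below is therefore an assumption.

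**Step 1: when does loss bias the comparison?** Let p be true response, dR the dropout among responders and dN the dropout among non-responders. The observed responder rate is

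p(1 − dR) / [p(1 − dR) + (1 − p)(1 − dN)].

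Take true response of 60% (UP-A) and 40% (TAU): difference 20 points, odds ratio 2.25.

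| Assumed loss | Observed UP-A | Observed TAU | Difference | Odds ratio |
|---|---|---|---|---|
| By arm only, 15% vs 37% | 60.0% | 40.0% | 20.0 | 2.25 |
| dR 16%, dN 36% in both arms | 66.3% | 46.7% | 19.6 | 2.25 |
| dR 16%, dN 36% in TAU; 26% at random in UP-A | 60.0% | 46.7% | 13.3 | 1.71 |
| dR 16%, dN 36% in TAU; reversed in UP-A | 53.3% | 46.7% | 6.7 | 1.31 |

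Example, TAU in rows 2–4: 0.4 × 0.84 = 0.336; 0.6 × 0.64 = 0.384; 0.336/(0.336 + 0.384) = 46.7%. The first two rows show that unequal rates alone, or one mechanism shared by both arms, do little or no harm. Bias needs the relation between loss and outcome to differ by arm.

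**Step 2: what can the week-8 score recover?** Simulation with 74 per arm, a normal latent outcome correlated with a week-8 score, logistic dropout on that score, and within-arm logistic imputation (20 imputations). Unless stated otherwise, TAU loses 30% with slope −1 per SD (worse progress, more loss), UP-A loses 20% at random, and true response is 45% vs 65%. In the no-effect rows response is equal in the two arms.

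| Scenario | Observed cases | Imputed from week-8 score |
|---|---|---|
| Correlation 0.6, true difference 20 | 13.9 points, power 32% | 19.5 points, power 57% |
| Correlation 0.6, no effect | type I error about 10% | about 5–6% |
| Correlation 0.3, true difference 20 | about 17 points | about 19.5 points |
| Correlation 0.3, no effect | type I error about 7% | about 5–6% |
| Correlation 0.6, no effect, opposite mechanisms, 25% loss each | type I error about 20% | about 6% |
| Correlation 0.6, true difference 20, same mechanism in both arms | no bias | no bias, no loss of power |

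A milder case (slope −0.5, correlation 0.4) gives 18.0 points and type I error of about 5% on observed cases.

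**Step 3: how large may the imputation model be?** At 30% loss, TAU keeps 74 × 0.70 ≈ 52 observed youths. At correlation 0.6, imputing by arm from 17 correlated scores recovered only about 17.0 to 17.7 points; a three-score set recovered 19.3. Where both arms shared the same mechanism, the 17-score model pulled the estimate from 19.3 to 17.5 points and power from 56% to 48%. An overfilled model creates its own bias.

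**The case against.** The strongest reply is that the plan is silent rather than wrong. A reader might infer that it discards everyone who leaves treatment before week 16. The documents do not say that. Voluntary leavers may still be assessed. The windows run to 4 weeks after the post-treatment date and 8 weeks after the follow-up date, and later data can still be collected (section 10). Assessments can be completed online, by phone or by Zoom (section 21). A youth who misses week 16 but is rated at follow-up can remain in a two-visit model. No week-8 CGI-I is being ignored, because none is scheduled.

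A reader might also infer that any arm difference in dropout biases the result. Step 1 shows otherwise. Hypothesis 3c makes differing engagement plausible, but no passage shows that loss will relate to progress differently by arm.

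The simulation has limits too. It compares risk differences in independent youths rather than fitting a clustered GLMM. It gives every lost youth a week-8 score, although some will leave before week 8. Its losses and slopes are assumed.

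All of this stands, and it makes the concern conditional. It does not remove it: post-withdrawal assessment is optional, clinic-discharged youths leave the study, and for a youth with neither rating the stated model has no information and no step to supply any.

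**Conclusion.** The point holds as a conditional weakness of the primary analysis. For youths without either CGI-I rating, the plan has no method, and it gives the relevant scores already collected no part in the primary comparison. If loss tracks poor progress differently by arm, the assumed main scenario costs about 6 points of a 20-point difference at correlation 0.6 and about 3 points at 0.3, with type I error of about 10% and 7%. Opposite mechanisms in the two arms are worse, at about 20%. If loss depends on arm alone, or on progress alike in both arms, little or nothing is lost. These sizes rest on assumed response rates, 20–30% loss and the stated slopes; the documents supply only the 74 per arm and the visit schedule. The change should be made because imputation from a small set of scores cost nothing in the shared-mechanism case and removed nearly all the bias in the others.

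**What to change.** Define the primary analysis on all randomised youths. Multiply impute missing CGI-I response at 16 weeks and follow-up, within arm or with arm-by-score interactions, from a small prespecified set: for example baseline CGI-S, one symptom composite per reporter at baseline and at week 8, and any observed CGI-I. Make the imputation model reflect whatever clustering the GLMM carries, and state that clustering. Fit the GLMM to each completed data set and combine the results. Include baseline CGI-S as a covariate in the GLMM; none of the figures above depends on that addition.

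Keep two sensitivity analyses: the observed-data GLMM, and one that counts a missing rating as non-response. Fix all of this before the outcome data are analysed.

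The cost is programming, including a clustered imputation model; no new data are needed. The gain will be small for youths who leave before week 8, or if week-8 scores predict response weakly.

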We estimate that each clinician will maintain a caseload of approximately four participants per condition annually. With a total of ranging from 3-9 clinicians per condition per site, we anticipate routine availability of new youth participant slots within two weeks of initial baseline assessment across conditions. If wait times become substantially uneven across conditions (e.g., adolescent participants waiting longer for a study clinician to become available in the TAU or TAU+ condition versus UP-A), additional clinicians (or clinics) may be added as needed to such conditions to ensure rapid randomization of participants. Clinician and adolescent participants who are randomized will either receive TAU, TAU+ or UP-A in a 1:1:1 ratio. We will use block randomization of adolescents within CMHC, blocked by presence of an adolescent depressive disorder (as assessed by the ADIS-5-C/P) and use of psychiatric medications (specifically, a SSRI, SNRI or benzodiazepine) at the time of study enrollment. If adolescents are randomized to a condition for which a clinician is not currently available (e.g., the clinician in that condition has a full caseload, the clinician in that condition does not have an appointment available at a time that works for the family, the clinician in that condition has left the study and has not yet been replaced), we will move down the randomization list until the adolescent can be assigned to a clinician. In the case of siblings, both youth will be randomized to the same condition and we will cross two rounds of that condition off the randomization list. A maximum of two adolescents from the same family may be admitted to the study.

Study Procedures:

Table 2 details the study Assessment Schedule and descriptions of measures are provided below. Once informed consent and assent has been obtained from caregivers and participants respectively, an initial study assessment to determine eligibility will take place as close as possible to the standard intake at the participating CMHC, prior to treatment initiation. Consent process will occur face to face at the CMHC, University, or at a private place within the

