- **Clinical Global Impression-Severity (CGI-S):** The CGI-S is a 7-point clinician rating of severity of psychopathology. Severity ratings range from 0 (no illness) to 6 (extremely severe).
- **Clinical Global Impression-Improvement (CGI-I):** The CGI-I is a 7-point rating of treatment response anchored by 1 (“very much improved) and 7 (“very much worse”).
- **Children’s Global Assessment Scale (CGAS):** The CGAS is a widely used 100-point rating scale used to measure global functional impairment.

Adolescent- and Parent-Rated Measures of Anxiety, Depression, and General Psychopathology:

- **Screen for Child Anxiety Related Emotional Disorders-Youth and Parent Reports (SCARED/-P):** The SCARED and SCARED-P are 41-item self- and parent-reports of anxiety severity across five domains: panic disorder, generalized anxiety disorder, separation anxiety disorder, social phobia, and school anxiety.
- **Mood and Feelings Questionnaire-Self and Parent Reports (MFQ):** The MFQ Self Report is a 33 item and the Parent Report is a 34 item youth mood and feelings scale that yields a total score.
- **Strengths and Difficulties Questionnaire- Self and Parent Reports SDQ):** The SDQ is a 25 item measure of youth psychopathology that yields a total score and five subscale scores: emotion problems, conduct problems, hyperactivity, peer problems, and prosocial. Separate versions are administered to youth and caregivers.

Measures of Parent Psychopathology and Emotion Regulation:

- **Patient Health Questionnaire-9 (PHQ-9):** The PHQ-9 is a 9-item parent report measure of parent depression symptoms rated on a 4-point Likert-type scale (0=Not at all, 1=Several days, 2=More than half the days, 4=Nearly every day). It yields a total score and rating of impairment.
- **Generalized Anxiety Disorder-7 (GAD-7):** The GAD-7 is a 7-item parent report measure of parent anxiety symptoms rated on a 4-point Likert-type scale (0=Not at all, 1=Several days, 2=More than half the days, 4=Nearly every day). It yields a total score and rating of impairment.

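### The primary responder GLMM names no baseline covariate; prespecifying baseline CGI-S would be a cheap improvement, with a gain that depends on how prognostic severity is

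*Combined protocol and SAP*

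**What the plan says.** The analysis plan is two sentences under Data Analysis Plan in section 12. The first proposes a GLMM with a logistic link "to examine treatment effects on the dichotomous primary outcome". The second assigns the continuous outcomes to ordinary multilevel models. Neither names a fixed effect, random effect, time term or covariate, and neither says that the model is unadjusted.

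On the outcome, section 9 states: "Response will be defined as a Clinical Global Impression-Improvement (CGI-I) of 1 or 2 at 16 weeks after treatment initiation", and again at the 3-month follow-up. Section 10 describes the two ratings: "The CGI-I is a 7-point rating of treatment response anchored by 1", while "The CGI-S is a 7-point clinician rating of severity of psychopathology", scored 0 to 6. In Table 2 the evaluator rates CGI-I only at 16 weeks and follow-up. CGI-S is rated pre-treatment and at both of those visits.

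On timing, Study Procedures in section 10 says: "Randomization will take place following this first assessment once subjects have been deemed eligible for participation". The same text describes the first assessment as "completion of some or all of the questionnaires/procedures listed in the" pre-treatment column, so a baseline CGI-S is scheduled for all but not assured for each youth. The abbreviated re-assessment for delayed starters does not list CGI-S.

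On balance, Randomization in section 10 says: "We will use block randomization of adolescents within CMHC, blocked by presence of an adolescent depressive disorder", and by use of certain psychiatric medications. Severity is not a factor.

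**The concern.** The continuous outcomes have pre-treatment values, so a longitudinal model for them could take in the baseline as a repeated measure. The primary outcome cannot be handled that way, because an improvement rating has no baseline. Unless a covariate is named, nothing in the primary model reflects how ill each youth was at entry, and nothing in the allocation scheme balances it.

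Entry requires a clinical severity rating of 4 or more on any of a range of anxiety and depressive disorders, or an adjustment disorder, so severity can vary. If it predicts response, leaving it out gives up some efficiency and leaves each comparison open to whatever imbalance chance produces. If the covariate set is instead settled at analysis, the choice is made with the data in view. Either matters on a primary outcome with about 74 youths per arm.

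**Working it through.** **Inputs from the documents.** About 222 youths (section 6), allocated 1:1:1 (section 10): 222 / 3 = 74 per arm.

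**Inputs assumed.** The documents give no alpha, power, response rates, clustering coefficient, dropout or strength of association between baseline severity and response, so there is no figure of the plan's own to reproduce. Assumed here: two-sided 5%, response 40% v 60%, and a log odds ratio g per SD of severity from 0 to 1.0. By formula, 74 per arm then has 68.5% power.

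**Step 1: chance imbalance between two arms.** In SD units, the difference in mean severity has standard deviation sqrt(2/74) = 0.164. P(|difference| > 0.2) = 2[1 - Φ(0.2/0.164)] = 0.224, or about 22%. Among those comparisons the mean size of the imbalance is 0.164 × φ(1.22)/[1 - Φ(1.22)] = 0.164 × 0.190/0.112 = 0.28 SD.

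**Step 2: what such an imbalance does.** Roughly, the response difference shifts by 0.28 × g × p(1 - p). With p = 0.4, p(1 - p) = 0.24, giving 0.013 at g = 0.2, 0.034 at g = 0.5 and 0.067 at g = 1.0. The simulated values in the table are close, and somewhat lower at large g because averaging over severity flattens the curve. After adjustment the remaining error was 0.3 points or less for g of 0.5 to 1.0.

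**Step 3: variance and power.** Single-level logistic simulations, 4,000 to 8,000 trials per setting, standard normal severity. The variance ratio is adjusted over unadjusted, for the standardised response difference.

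| g (log OR per SD) | Variance ratio | Power, unadjusted to adjusted | Error when imbalance > 0.2 SD, unadjusted | SE of log OR |
|---|---|---|---|---|
| 0 | 1.006 | 70.8% to 68.6% (Wald) | none expected | 0.338 to 0.341 |
| 0.2 | 0.999 | 69.2% to 67.8% | 1.4 points | not tabulated |
| 0.3 | 0.991 | 70.0% to 69.8% | 1.8 points | not tabulated |
| 0.5 | 0.946 | 71% to 71% | 3.1 points | 0.338 to 0.352 |
| 0.7 | 0.903 | 72% to 74% | 4.5 points | 0.338 to 0.363 |
| 1.0 | 0.837 | 70% to 76% | 5.9 points | 0.338 to 0.381 |

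Power is by likelihood-ratio test except in the first row. Repeat simulations gave variance ratios within about 0.02 of these; one gave 70.7% to 77.7% power at g = 1.0.

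**Step 4: check by hand.** The variance ratio should be close to 1 - r², where r is the within-arm correlation of severity with response.
- Odds ratio 1.5 per SD, r = 0.19: 1 - 0.036 = 0.964; simulated 1/1.03 = 0.971.
- Odds ratio 2.0 per SD, r = 0.31: 1 - 0.096 = 0.904; simulated 1/1.087 = 0.920.
- Odds ratio 3.0 per SD, r = 0.43: 1 - 0.185 = 0.815; simulated 1/1.226 = 0.816.

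**Step 5: type I error.** At 40% v 40% it was 5.1% to 5.8% unadjusted and 4.5% to 5.6% adjusted.

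**Step 6: a coarser covariate.** CGI-S is an integer scale. With an assumed three-category version the ratios at g = 0.5, 0.7 and 1.0 become 0.968, 0.931 and 0.863, and power goes from 71.4% to 70.6%, 73.1% to 73.7% and 71.1% to 74.3%.

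**The case against.** The strongest reply is that nothing here is shown to be wrong. The plan is silent on covariates altogether. A reader might infer that the sponsor chose an unadjusted analysis, but the text does not say so; what it supports is that the covariate set is unspecified. That stands. Silence is no safer, though: either the model is fitted as written, or the covariates are chosen later. Naming them now settles both.

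Second, the gain may be nil. CGI-I rates improvement, so it already takes the starting state into account, and the documents give no association with baseline CGI-S. Below a log odds ratio of about 0.3 per SD, Step 3 shows no useful variance gain and slightly lower power. This stands, and it is why the result is a range.

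Third, a reader might infer that omitting severity widens the interval for the planned odds ratio. It does not: the standard error of the log odds ratio rises with adjustment, because the adjusted odds ratio is a different and larger quantity. The variance gain belongs to the standardised response difference, which the plan does not currently report. This stands and shapes the fix.

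Fourth, the simulations are single-level, while youths are nested in clinicians and clinics, and they treat CGI-S as continuous. Both limits stand; Step 6 shows that a coarse scale shrinks the gain.

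**Conclusion.** The primary responder model names no baseline covariate, its outcome has no baseline value, and a severity rating scheduled before randomisation goes unused in it. Prespecifying that rating is a cheap improvement of minor to moderate weight.

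Over assumed log odds ratios of 0.2 to 1.0 per SD, adjustment changes the variance of the standardised response difference by 0% to about -16% and power by about -1 to +6 points. In the roughly 22% of two-arm comparisons with an imbalance above 0.2 SD, it removes about 1 to 6 percentage points of error. These figures rest on 74 v 74, response 40% v 60%, allocation independent of severity, and no clustering or dropout.

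Three stronger readings are not supported. The primary comparison is not biased on average and its type I error is not inflated; the error is conditional on the imbalance in the one trial that is run. It cannot be said that an arm that starts milder will look more effective, because on an improvement scale milder youths may have less room to improve, and the documents give no direction. Nor should the variance ratios be turned into a number of youths saved: the association is assumed, and the planned model estimates an odds ratio.

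**What to change.** In the Data Analysis Plan of section 12:

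- Name baseline CGI-S (the pre-randomisation value) as a fixed covariate in the responder GLMM for every arm comparison, together with the randomisation factors: CMHC, depressive disorder and medication use. Say whether CMHC enters as a fixed or a random effect.
- Report a standardised (marginal) response difference as well as the odds ratio, and say how it is averaged over covariates and random effects.
- State how a missing baseline CGI-S is handled, since the baseline battery may be only partly completed.
- Show the result without CGI-S as a sensitivity analysis.

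The cost is a few sentences, with no new data, visits or staff. CGI-S uses one degree of freedom and may lose about 1 to 2 points of power if severity turns out not to be prognostic. The randomisation factors use further degrees of freedom, which were not simulated.
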